6.4.6. Subgroup Analysis of Key Secondary Endpoints

Subgroup analysis of key secondary endpoints will follow the subgroups classification for primary efficacy endpoint in [Section 6.3.6](#).

The evaluation for binary endpoint will use the same approach as the primary efficacy endpoint ORR.

The evaluation for continuous endpoints will use a similar approach for the primary analysis of each key secondary endpoint, with the addition of three fixed factors (subgroup, subgroup-by-treatment and subgroup-by-treatment-by-time) into the corresponding MMRM model.

6.5. Other Secondary Efficacy Analyses at the End of Study Part 1

6.5.1. Tumor Responses by Investigators

In addition to tumor responses by BIRC based on both RECIST v1.1 and TVS, the best overall response (BOR) based on RECIST v 1.1 will be determined programmatically using overall time point responses by investigators up until the last evaluable visit response at Day 1 of Week 25 visit prior to or on the date of (i) radiographic progression as defined by RECIST v1.1; or (ii) withdrawal of consent to obtain scans; or (iii) receiving subsequent anti-cancer therapy or surgery, whichever is earlier.

Statistical Analysis Plan for Protocol ABSK-021-301

Investigator-25-Week ORR will be calculated as the proportion of patients with either CR or PR (i.e., responders) as the response by the Investigator within 25 Weeks based on RECIST v1.1 criteria. The calculation will follow the same rule as the primary endpoint of BIRC-25-Week ORR. The response status within 25 weeks (i.e., BOR) will follow [Table 6.1](#) based on the tumor response at Week 13 and Week 25.

The number and percentage of patients in each category of BOR based on investigators' tumor assessments (CR, PR, SD, non-CR/non-PD, PD, or NE) will be presented for the ITT analysis set. The associated exact 95% two-sided CIs using Clopper-Pearson method will be computed for ORR.

Detailed tumor assessment data from investigators will be listed along with derived response for all randomized patients.

The best percent change from baseline in the sum of diameters of target lesions will be summarized using descriptive statistics (n, mean, standard deviation, median, minimum, and maximum). Additionally, the best percent change from baseline in the sum of diameters of target lesions of individual patients and BOR will be plotted by treatment groups using a waterfall plot. A swimmer plot of the overall response and treatment duration will be provided.

The Investigator-25-Week ORR based on RECIST v1.1 will be based on the ITT analysis set and analyzed using the same method as the primary endpoint.

To compare discrepancy of response assessments, a summary of concordance between the BICR and Investigator review of radiographic images will be provided.

6.5.2. Duration of Response (DOR)

In general, the DOR for responders is defined as the time interval between the date of the first documentation of objective response (CR/PR) and the date of first documentation of radiographic disease progression, or death, whichever occurs earlier.

$$\text{DOR (months)} = [\text{date of event/censoring} - \text{date of the first qualifying response} + 1] / 30.4375$$

Patients who have no record of documented disease progression or death at the time of data cutoff date for a planned analysis will be censored according to the rules detailed in [Table 6.3](#).

The following DORs will be derived for all patients with an objective response in Part 1.

- DOR by BIRC based on RECIST v1.1
- DOR by BIRC based on TVS
- DOR by Investigator based on RECIST v1.1

Analysis of DOR will be conducted for patients with an objective response in the ITT analysis set. The 25th, median, 75th percentile of the time, and their associated 95% CIs (Brookmeyer and Crowley¹¹, 1982) will be estimated using Kaplan-Meier method adjusting for censoring. In addition, the probability of DOR at landmarks of month 3, 6, 9 and 12 and their corresponding two-sided 95% CIs (Kalbfleisch¹², 1980) will be provided.

Furthermore, the number of patients who have an ongoing response with DOR ≥ 6 months and ≥ 12 months and the number of patients on follow-up will be summarized by treatment group.

Table 6.3 Censoring Rules for DOR

Statistical Analysis Plan for Protocol ABSK-021-301

Situation	Date of Progression or Censoring	Outcome
Documented progression or death	Date of progression (or death)	Progressed
Death without documented progression between scheduled tumor assessments	Date of death	Progressed
No documented progression and no death	Date of last adequate tumor assessment	Censored
Documented progression or death after exactly one missing assessment	Date of progression (or death)	Progressed
Documented progression or death after more than one consecutive missed assessment visits	Date of last adequate tumor assessment prior to the first missed visit	Censored
Treatment discontinuation for toxicity or other reason (i.e., not due to documented progression)	Ignore the treatment discontinuation and follow situations above (ITT approach)	As per above situation
New anticancer treatment started prior to documented progression	Date of last adequate tumor assessment prior to the start of new anticancer treatment	Censored

6.5.3. European Quality of Life 5 Dimensions – 5 Levels (EQ-5D-5L)

The EQ-5D-5L are administered at Screening, Week 1, Week 5, Week 9, Week 13, Week 17, Week 21, and Week 25 during Part 1. The instrument consists of 2 pages: the EQ-5D descriptive system and the EQ visual analogue scale (VAS). A copy of the questionnaire is provided in protocol Appendix Section 12.7.

The questionnaire will be analyzed according to the recommendations of the authors (www.euroqol.org). The descriptive system contains 5 dimensions (mobility, self-care, usual activities, pain/discomfort, and anxiety/depression), each with 5 response categories (no problems, slight problems, moderate problems, severe problems, and extreme problems). The number and percentage of patients in each response category will be tabulated by visit by treatment group. Percentages are based on the number of patients for whom an assessment is provided at the respective visit.

The EQ visual analogue scale is a visual scale from 0-100 to record a respondent's overall self-rated health state. The respondent is asked to mark an 'X' on the scale then record the corresponding number; 0 refers to the worst possible health state, 100 refers to the best possible

Statistical Analysis Plan for Protocol ABSK-021-301

health state. The EQ VAS will be summarized for the observed response and change from baseline by visit by treatment group.

The change from baseline in EQ-VAS score at Week 25 will be analyzed using similar MMRM models as for BPI. Missing data will not be imputed. The least squares mean (LSMEAN) for each treatment, and treatment difference (ABSK021 – Placebo) in LSMEAN along with its' 95% CI and p-value will be provided for each scheduled visit.

6.6. Final Efficacy Analyses at the End of Study Part 2

6.6.1. Long-Term ORRs and DORs

To evaluate the treatment effect beyond 24 weeks, all three ORRs will be thoroughly analyzed based on the ITT analysis set.

- BIRC-ORR based on RECIST v1.1
- BIRC-ORR based on TVS
- Investigator-ORR based on RECIST v1.1

To minimize biased evaluations beyond Part 1, the BIRC and Investigator will remain blinded to the treatment assignment after unblinding study for the Part 1 primary analysis.

The BIRC will provide two sets of tumor response assessments based on the Part 1 and Part 2 baselines for all patients irrespective of treatment assignment in Part 1, respectively. In the case of patients who have been switched to the ABSK021 treatment after receiving a placebo, their Part 2 BIRC-ORR evaluations based on their Part 2 baseline tumor assessments will be included in the analysis of ORR. On the other hand, the patients who were randomized to ABSK021 in Part 1 will remain unchanged.

However, investigators will evaluate the patient's tumor responses based on the initial assessment done in Part 1, regardless of their treatment assignment. For this reason, for those patients who have been switched to the ABSK021 treatment after receiving a placebo, their overall visit response by RECIST v1.1 during subsequent tumor assessment visits after Part 1 will be determined programmatically based on the Part 2 baseline measurements of tumor size and subsequent information collected on the electronic case report form (eCRF) regarding the investigator's measurement of target lesions (TL), non-target lesions (NTLs) and new lesions. On the other hand, for patients who were randomized to ABSK021 in Part 1, investigators' evaluations of tumor responses for each visit will be used in the analysis.

These ORRs and associated BORs by BIRC and Investigator will be descriptively summarized by randomized treatment group sequence as defined in [Section 4.3.2](#) along with their exact two-sided 95% CIs using the Clopper-Pearson method.

Corresponding DORs for above-mentioned ORRs will be derived. These DORs will be summarized in the same approach as described above.

6.6.2. Other Final Efficacy Analyses

In addition to the long-term ORR and DOR mentioned above, other assessments beyond Part 1 will be summarized for long-term efficacy at each visit until completion of the study unless otherwise specified.

- Change from baseline in relative ROM;
- Change from baseline in Worst-Stiffness-NRS scores;
- Change from baseline in BPI Worst Pain NRS scores;
- Change from baseline in PROMIS-PF scales;
- EQ-5D-5L health profile in 5 dimensions (mobility, self-care, usual activities, pain/discomfort, and anxiety/depression)
- Change from baseline in EQ-5D-5L VAS

If patients switched to the ABSK021 treatment group after receiving a placebo in Part 1, their baselines will be derived from the latest non-missing assessments prior to or on the date of the first dose in Part 2. Descriptive statistics will be provided for each randomized treatment group sequence as defined in [Section 4.3.2](#). These include the number of observations, mean, standard deviation, 95%CI, median, minimum, and maximum for continuous endpoints; and frequencies and percentages with 95% CI using the Clopper-Pearson method for binary endpoints.

7. SAFETY ANALYSIS**7.1. General Consideration of Safety Analysis**

Safety analyses will be conducted for each planned analysis based on the data group specified in [Table 4.7](#).

Safety evaluations will be based on the incidence, severity, and type of AEs, and changes in the patient's ECOG, vital signs, ECG findings, clinical laboratory results (hematology, blood chemistry, urinalysis, myocardial enzyme test, coagulation, thyroid function tests), Echocardiography/MUGA, and NCI-PRO-CTCAE (Part 1 only). Missing safety data will generally not be imputed, unless otherwise specified.

Safety summaries will include only on-treatment assessments/events. An on-treatment assessment is defined as any assessment that is evaluated between the date of first dose of study drug and the date of last dose of study drug + 30 days. If the last dose date of study drug is missing, any assessment occurring after the start of study drug will be considered as on-treatment.

Safety analyses will be based on the Safety Analysis Set. All available safety data up to each planned data-cutoff date will be summarized by treatment group. This summary will include all relevant safety data obtained throughout the on-treatment period for each respective group as outlined in [Table 4.7](#).

In the evaluation of safety data for those patients switching from the blinded Placebo group to the open-label ABSK021 group in Part 2, the baseline value will be determined based on the last non-missing measurement recorded before the date of the first ABSK021 dose in Part 2.

Statistical Analysis Plan for Protocol ABSK-021-301

Generally, no inferential statistical testing is planned on the safety data, unless otherwise specified. Visit-based safety summaries will present data at each scheduled analysis visit that defined in [Section 4.2.4](#), maximum/minimum post-baseline. Any worst-case (including maximum and minimum) summaries will be based on extreme values falling in the category from both scheduled and unscheduled visits during the on-treatment period. Patients with High and Low values for Normal Ranges at any post-baseline visits for safety parameters will be counted in both the High and Low categories of “Any visit post-baseline” row of related summary tables. This will also apply to relevant Potential Clinical Importance summary tables.

Listings will display all values collected at each time point along with change from baseline for continuous variables. If the average of replicates is derived for any analysis (i.e., ECG), the corresponding listings will include both replicates and average. Listings will include both planned visit and derived analysis visit with a flag for the record included in summaries. For any incomplete AE onset or end date, the imputed date and raw date will be listed.

7.2. Adverse Events

7.2.1. Coding and Grading of AEs

AEs will be collected from the time of signed informed consent throughout the treatment period and up to 30 days after the last dose of study treatment. All AEs will be coded to primary System Organ Class (SOC) and Preferred Term (PT) according to the latest version of Medical Dictionary for Regulatory Activities (MedDRA). The severity (toxicity grades 1-5) of AEs will be graded according to the National Cancer Institute (NCI) Common Terminology Criteria for Adverse Events (CTCAE) version 5.0 by investigators.

7.2.2. Classifications of AEs

Treatment-emergent adverse event (TEAE) is defined as any AE that occurs after administration of the first dose of study drug and through 30 days (inclusive) after the last dose of study drug, any event that is present at baseline but worsens in severity or is considered treatment-related by the Investigator after administration of the first dose of study drug. AEs with start/end dates that are partially/completely missing will be imputed according to the specifications in [Appendix 1](#) to classify TEAEs.

Any TEAE will be defined as drug-related for related relationship to study drug judged by the investigator. Every attempt will be made to obtain complete information for AEs regarding severity (i.e., CTCAE Grade) and relationship to drug; however, in the rare case of missing data, missing AE relationship will be classified as “Related” in summary tables. The non-imputed raw data will be presented in AE listings.

7.2.3. Adverse Events of Clinical Interest (AECI)

The AECI categories will be identified by the following search criteria per Standard MedDRA Queries (SMQs)/Company MedDRA Queries (CMQs) in [Appendix 4](#). The study medical team will provide the preferred terms for identifying Adverse Events of Clinical Interest (AECIs)

before the primary database lock (DBL) for the end of Part 1 analysis. Any additional preferred terms identified after the primary DBL will be added as an addendum to the SAP.

7.2.4. AE Summary

Only TEAEs will be summarized by treatment group and pre-defined group (see [Section 7.1](#) for details). All AEs will be listed with a flag of prior-treatment, TEAE, post-treatment (if any).

First, a high-level overall summary table for overall TEAEs will be produced by presenting the number and percentage of patients with at least one specific TEAE in any of the following categories:

- Any TEAEs
- Any drug-related TEAEs
- Any TEAEs with CTCAE grade ≥ 3
- Any drug-related TEAEs with CTCAE grade ≥ 3
- Any TEAEs resulting in death
- Any drug-related TEAEs resulting in death
- Any serious TEAEs
- Any drug-related serious TEAEs
- Any TEAEs leading to dose reduction
- Any TEAEs leading to dose interruption
- Any TEAEs leading to dose reduction/interruption
- Any TEAEs leading to discontinuation of treatment
- Any drug-related TEAEs leading to discontinuation of treatment

For overview summary of TEAE, the Exposure-Adjusted-Incidence-Rate (EAIR) will also be provided for each item. The EAIR per 100 patient year is defined as follows:

- $EAIR = 100 * \frac{n_{TEAE}}{(\sum_{i=1}^{n_{TEAE}} t_i + \sum_{j=1}^{n_{noTEAE}} t_j) / 365.25}$
- $t_i = (\text{date of first occurrence} - \text{date of first exposure}) + 1$

If cutoff date is earlier than end of treatment:

- $t_j = (\text{earliest of } (\text{date of last exposure/cutoff} + 30, \text{date of death}) - \text{date of first exposure}) + 1$

If cutoff date is later than end of treatment:

- $t_j = (\text{earliest of } (\text{date of last exposure} + 30, \text{date of death, date of cutoff}) - \text{date of first exposure}) + 1$

Where n_{TEAE} is the number of patients with specific AE. t_i is the exposure time up to the first occurrence of event for these patients with specific AE. n_{noTEAE} is the number of patients who did not experience specific AE and t_j is the time at risk for them.

The EAIR and its 95% Confidence Intervals (CIs) [if 4 or more patients with specific TEAE in any of the treatment groups] will be presented (Xin He, et. al., 2015)¹³.

In addition, the number of events will be summarized for the following AE categories:

Statistical Analysis Plan for Protocol ABSK-021-301

- Serious TEAEs including incidence of SAEs based on individual components of the SAE criteria
- TEAE leading to discontinuation of study drug
- TEAE leading to dose modification, including subcategories of dose interruption, and dose reduction

TEAEs in selected categories above will be summarized by presenting the number and percentage of patients having at least one TEAE in each primary SOC or each PT as outlined under the table below. A patient with multiple occurrences of an TEAE associated with a specific SOC or PT within a SOC will be counted only once within the SOC or PT within a SOC, respectively.

For TEAE summaries presented by CTCAE grade, a patient with multiple grades for a TEAE will be summarized under the maximum grade recorded for the event. For drug-related TEAE summaries, a patient with multiple causalities for a TEAE will be considered related as long as assessed as related at least on one occasion by investigators.

In TEAE summaries the primary SOC and PT within a SOC will be presented in descending order based on the incidence and PT alphabetical order across all patients. The incidence rate of AE will be calculated using the number of patients within each specified treatment group as the denominator.

The following table summarizes the planned analyses, including selective subgroup analyses.

TEAEs Tabulated by:	Any TEAE	TR-TEAE	TESAE	TR-TESAE	AECI
System Organ Class and Preferred Term	▲ a, b, d	▲ a, b, d	▲	▲	
Preferred Term	▲ a,c	▲ a,c			▲ ^a
PT and Maximum CTCAE Grade	▲	▲			▲

TR-TEAE: treatment-related TEAE; TESAE: Treatment emergent SAE; TR-TESAE: treatment-related TESAE.

[a] Repeat for: of grade 3 or higher

[b] Repeat for: leading to discontinuation of treatment, dose reduction/dose interruption/modification.

[c] Repeat for: Resulting in death.

[d] Selective Subgroups

In addition, summaries of most common TEAEs and most common TEAEs with any CTCAE grade 3 or 4, showing all events that occur in at least 5% of patients in any treatment group will be summarized by preferred term. This 5% cut-off may be modified after review of the data.

For AECI, an overview summary table will be provided including number and percentage of patients having at least one AECI event, at least one AECI with maximum CTCAE grade, at least one ongoing AECI event, at least one resolved AECI event, at least one serious/non-serious AECI event and at least one action taken (dose reduction/interruption, discontinuation of treatment) to AECI events. Time to first onset any grade / grade ≥ 3 and resolution of AECI events will be summarized descriptively.

The following AE listings will be flagged with TEAE, prior-treatment or post-treatment.

- All serious AEs

Statistical Analysis Plan for Protocol ABSK-021-301

- AEs leading to discontinuation of any study drug
- AEs leading to deaths
- All AECIs

Additionally, overdose (MedDRA HLT “Overdoses NEC”) and medication errors (MedDRA SMQ (narrow) “Medication errors”) will be summarized by PT. Drug interactions (MedDRA HLT “Interactions”) will be summarized by PT. Drug abuse (MedDRA SMQ (narrow) “Drug abuse and dependence”) will be summarized by PT. Withdrawal and rebound includes MedDRA HLT “Withdrawal and rebound effects”.

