28. The PROMIS Physical Functioning Scale and the EQ-5D-5L Health Scale will be assessed during the screening period (within 14 days prior to randomization), on C1D1 (-1 day), C2D1 (± 7 days), C3D1 (± 7 days), C4D1 (± 7 days), C5D1 (± 7 days), C6D1 (± 7 days) and C7D1 (± 7 days), respectively. C1D1 assessments should be completed prior to dosing. The mean score of evaluations during the screening period (within 14 days prior to randomization) and on C1D1 will be used as baseline. The PROMIS Physical Functioning Scale includes two different sets of topics for the upper and lower extremities. Items assessing lower extremity function will be used for patients with lower extremity tumors, and the items for assessing upper extremity function will be used for patients with upper extremity tumors. On visit days when scales are required, including the screening period, it is recommended to be completed before any invasive clinical procedure is performed. Even if a patient experiences disease progression or discontinues treatment, PROMIS Physical Functioning Scale and the EQ-5D-5L Health Scale are recommended to be completed from baseline up to week 25.

29. NCI-PRO-CTCAE will be assessed during the screening period (within 14 days prior to randomization), on C1D1 (-1 day), C1D8(± 1 days), C1D15 (± 1 days), C1D22 (± 1 days), C2D1 (± 2 days), C2D8(± 2 days), C2D15 (± 2 days), and C2D22 (± 2 days), C3D1 (± 7 days), C4D1 (± 7 days), C5D1 (± 7 days), C6D1 (± 7 days), C7D1 (± 7 days), and EOT visit respectively.
30. Patient who completed the C7D1 visit of Part 1 will be further confirmed by the investigator whether to enter Part 2 and receive treatment with open-label ABSK021. Patients need to meet eligibility criteria to continue in Part 2. The investigator will comprehensively evaluate the benefits and risks of the patient entering Part 2, and make the final decision based on the principle of maximizing the patient's benefit-risk ratio. In principle, a maximum of 28 days is allowed from the end of C7D1 follow-up in Part 1 to entry into Part 2.

Table 2: Schedule of Events - Part 2

Study Procedure	Cycle 1 ¹	Cycle 2	Cycle 3	Cycle 4 ²	Cycle 7	End of Treatment Visit (EOT Visit) ³	Safety Follow-up ⁴	Progression Follow-up ⁵
	C1D1 (- 2 days)	C2D1 (± 7 days)	C3D1 (± 7 days)	C4D1 (± 7 days)	C7D1 (± 7 days)			
	Week 25	Week 29	Week 33	Week 37	Week 49			
Part 2 eligibility confirmation ¹	X							
Physical examination/ECOG score ⁶	X	X	X	X	X	X		
Vital Signs ⁷	X	X	X	X	X	X		

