4.3.2. Study Treatment Groups Presentation

The summary of study data will include all relevant data obtained throughout a specific study period for the following respective patient groups. The grouping of patients for efficacy and safety data will be primarily based on the randomized treatment and the actual treatment received in Part 1, respectively, and whether patients received at least one dose of open-label ABSK021 beyond Part 1. The groups included in a specific table, figure, and listing (TFL) depend on their primary purpose and analysis stages.

Statistical Analysis Plan for Protocol ABSK-021-301

Table 4.6 Efficacy Data Display of Study Treatment Groups

Part	SAP		CSR Report	
	Description	Data inclusion	TFL Display (Order)	Included in Analysis
Part 1	Randomized Placebo in Part 1	Data from patients who were randomized to Placebo during Part 1 before their first dose in Part 2	Placebo P1 (1)	Primary analysis* Final analysis*
	Randomized ABSK021 in Part 1	Data from patients who were randomized to ABSK021 during Part 1 before their first dose in Part 2.	ABSK021 P1 (2)	Primary analysis Final analysis
Part 2 and Part 3	Placebo Switch to ABSK021	Part 2 and Part 3 data from patients who switched from blinded Placebo to open-label ABSK021 in Part 2	Switched to ABSK021 P2+P3 (3)	Primary analysis Final analysis
Part 1, 2 and Part 3	Randomized ABSK021 with longer follow up	Parts 1- 3 data up to the DCO from the patients who were randomized to ABSK021 in Part 1	ABSK021 P1-P3 (4)	Primary analysis Final analysis
Part 1, 2 and Part 3	All ABSK021 Treated	Parts 1-3 data up to the DCO from patients who received at least 1 dose of ABSK021	All ABSK021 Treated P1-P3 (5)	Primary analysis Final analysis End of study analysis

*Note: the primary and final analyses are defined in [Section 2](#).

Statistical Analysis Plan for Protocol ABSK-021-301

Table 4.7 Safety Data Display of Study Treatment Groups

Part	SAP		CSR Report	
	Description	Data inclusion	TFL Display (Order)	Included in Analysis
Part 1	Received Placebo in Part 1	Data from the patients who received blinded Placebo during Part 1 before their first dose in Part 2	Placebo P1 (1)	Primary analysis* Final analysis*
Part 1	Received ABSK021 in Part 1	Data from the patients who received blinded ABSK021 in Part 1 before their first dose in Part 2	ABSK021 P1 (2)	Primary analysis Final analysis

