7.4. Vital Signs

7.4.1. Vital Sign Parameters

Vital signs including pulse rate, respiration rate, body temperature, systolic blood pressure (SBP), diastolic blood pressure (DBP); weight and height will be measured according to Schedule of Study Assessments in the protocol.

Change from baseline for each parameter will be derived. The potentially clinically significant findings of vital signs and weight will be defined based on criteria in [Table 7.1](#). Both scheduled and unscheduled assessments will be used to identify the worst post-baseline values.

Table 7.1 Potentially Clinically Significant Criteria for Vital Signs and Weight

Vital Sign Parameter	Potentially Clinically Significant Criteria	
	Value Categories	Change from Baseline Categories

Statistical Analysis Plan for Protocol ABSK-021-301

SBP	≥ 120 mmHg	Increase ≥ 40 mmHg
	≥ 140 mmHg	Decrease ≥ 40 mmHg
	≥ 160 mmHg	
	≥ 180 mmHg	
	< 90 mmHg	
	≥ 120 mmHg and increase from baseline ≥ 20 mmHg	
DBP	> 90 mmHg	Increase ≥ 20 mmHg
	> 110 mmHg	Decrease ≥ 40 mmHg
	≥ 120 mmHg	
	≤ 60 mmHg	
	≥ 80 mmHg and increase from baseline ≥ 20 mmHg	
Pulse Rate	≥ 110 bpm	Increase ≥ 40 bpm
	≤ 50 bpm	Decrease ≥ 40 bpm
	≥ 120 bpm and increase from baseline ≥ 15 bpm	
	≤ 50 bpm and increase from baseline ≥ 15 bpm	
Weight	n/a	Increase $\geq 10\%$
		Decrease $\geq 10\%$
Respiratory Rate	> 20 breaths/min	
	< 12 breaths/min	

Note: bpm = beats per minute

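### SAP 7.2.4 counts up to 30 days after the data cut-off as time at risk for event-free patients still on treatment, which lowers the EAIR in columns with ongoing patients

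*SAP*

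**What the plan says.** SAP 7.2.4 (AE Summary) gives an EAIR per 100 patient-years for each of the 13 TEAE categories in the overview table. The denominator has two parts.

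- For patients with the event, t_i "is the exposure time up to the first occurrence of event for these patients with specific AE".
- For patients without it (their count "is the number of patients who did not experience specific AE"), t_j is time at risk, and its definition has two branches.
  - Branch 1 is headed "If cutoff date is earlier than end of treatment". Time ends at the earlier of "date of last exposure/cutoff" plus 30 days and death.
  - Branch 2 covers patients whose treatment ended before the cut-off. Time ends at the earliest of last exposure plus 30 days, "date of death, date of cutoff".

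SAP 7.1 limits each safety summary to data available up to the planned cut-off. SAP 5.6.1 also stops the duration of exposure at the cut-off.

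SAP 4.3.2, Table 4.7, defines the placebo Part 1 column as "Data from the patients who received blinded Placebo during Part 1 before their first dose in Part 2". The ABSK021 Part 1 column is defined in the same way. On the gap between parts, footnote 30 to the Part 1 schedule in the protocol says: "In principle, a maximum of 28 days is allowed from the end of C7D1 follow-up in Part 1 to entry into Part 2".

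In SAP 7.4.1, Table 7.1, one pulse-rate criterion reads "≤ 50 bpm and increase from baseline ≥ 15 bpm".

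**The concern.** Every day in the denominator of an incidence rate should be a day on which an event could have entered the numerator. Branch 1 breaks that rule. A patient still taking study drug at the cut-off has no countable event after that date, yet is credited with up to 30 more days. Branch 2 has the missing cap, so the two branches disagree with each other.

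The effect is downward and relatively largest where ongoing exposure is short. Among the affected columns that points to patients switched from placebo, at the primary analysis. The less frequent categories suffer most, because only event-free patients receive the credit.

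A second mismatch concerns the Part 1 columns. Their events stop at the first Part 2 dose, but branch 2 lets time run to last exposure plus 30 days, with caps only at death and cut-off.

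**Working it through.** The documents state no EAIR value, so there is no figure to reproduce. Exposure times, event counts and event times below are assumptions.

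**1. Where branch 1 can apply.** The primary cut-off is the last patient's Week 25 visit (SAP 2.1). Part 1 treatment is over for everyone by then, so the Placebo P1 and ABSK021 P1 columns hold nobody on Part 1 treatment. The end-of-study analysis follows Part 3 (SAP 2.3), when nobody is on treatment. That leaves the three columns with open-label data at the primary and final analyses.

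**2. Literal t_j.**
- Patient ongoing at a cut-off on Day 169: 169 + 30 = 199 days; 169 with a cap.
- Patient whose last Part 1 dose was on Day 168, one day before that cut-off: 169 days, because branch 2 caps.

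If the last recorded dose falls d days before the cut-off and that date is used, the credit is 30 - d days; hence up to 30.

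**3. Rare event, all patients ongoing at T days.** Ratio of the rate as written to the capped rate = T/(T + 30).

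| T (assumed) | Ratio | Bias |
|---|---|---|
| 28 | 28/58 = 0.483 | -51.7% |
| 84 | 84/114 = 0.737 | -26.3% |
| 168 | 168/198 = 0.848 | -15.2% |
| 336 | 336/366 = 0.918 | -8.2% |

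**4. Common event.** Under a constant hazard with cumulative incidence p by time T, λ = -ln(1 - p)/T and mean person-time is PT = p/λ. With a share f of event-free patients ongoing, the ratio is PT/(PT + f(1 - p)30). Take p = 94.6% (any TEAE at 50 mg QD in the Phase 1 study, Protocol 1.2.2) and f = 1. The bias is -5.6% at 84 days, -2.9% at 168 and -1.5% at 336. With f = 0 it is zero.

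**5. Group example.** 30 switched patients, 2 with an event at Day 40, the other 28 ongoing at 84 days.
- Capped: 2×40 + 28×84 = 2,432 days; 100×2×365.25/2,432 = 30.0 per 100 patient-years.
- As written: 2×40 + 28×114 = 3,272 days; 22.3 per 100 patient-years (-25.7%).

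**6. Part 1 columns (separate mechanism).** 30 placebo patients, 3 events at Day 84, and 27 event-free with their last Part 1 dose on Day 168. All 27 enter Part 2 and none is near the cut-off. As written, time is 27×198 + 3×84 = 5,598 days, or 19.6 per 100 patient-years. Time within the column depends on the drug-free gap before the first Part 2 dose:

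| Gap (days) | Time in column (days) | Bias as written |
|---|---|---|
| 0 | 27×168 + 252 = 4,788 (22.9 per 100 patient-years) | 4,788/5,598 - 1 = -14.5% |
| 14 | 27×182 + 252 = 5,166 | 5,166/5,598 - 1 = -7.7% |
| 28 | 27×196 + 252 = 5,544 | 5,544/5,598 - 1 = -1.0% |

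The protocol counts its 28 days from the C7D1 visit, so the gap from the last dose can differ by a few days.

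**7. Pulse flag.** A post-baseline value of at most 50 bpm after a rise of at least 15 bpm needs a baseline of 50 - 15 = 35 bpm or less.

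**The case against.** The strongest reply is that little rests on EAIR. It appears in one overview summary beside counts and percentages, and SAP 7.1 plans in general no inferential testing of safety data. That stands: no test or primary conclusion depends on it.

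A reader might infer that every EAIR in the study is understated. The documents do not support that. Branch 1 cannot reach the randomised Part 1 columns or the end-of-study analysis. One feature even pushes the other way. SAP 2.1 includes safety follow-up for patients who do not enter Part 2, while branch 2 stops their time at the cut-off. If events after the cut-off are counted for them, their rate is too high.

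A reader might also take the switched group's rate to be roughly halved. That needs every switched patient to have only about 28 days of exposure. The documents give no recruitment period, and because the cut-off is the last patient's Week 25 visit, earlier patients will have been exposed for longer.

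On the Part 1 columns, SAP 7.1 ties safety summaries to the groups in Table 4.7, so time could be read as bounded there too. The formula lists its limits explicitly, however, and the first Part 2 dose is not among them. The overrun affects both arms, so their rate ratio should change little, though it need not cancel exactly because only event-free patients receive it. For patients who never enter Part 2, the 30 days after the last dose are legitimate on-treatment time. The -14.5% is therefore an upper case. Immediate rollover is possible, since footnote 19 to the protocol's Part 2 schedule allows Part 2 drug to be dispensed on the day the Part 1 C7D1 visit is completed.

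Nor would a dead pulse flag hide bradycardia. Table 7.1 separately reports pulse at or below 50 bpm and falls of at least 40 bpm, and Table 7.2 reports ECG heart rate below 50 with a fall of more than 25%.

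**Conclusion.** The definition is wrong as written, within a limited scope. Branch 1 adds up to 30 uncountable days for event-free patients still on treatment and so biases EAIRs low in the three columns that contain them, at the primary and final analyses. The size depends on exposures that the documents do not give. It runs from about -52% to -8% for a rare event with all patients ongoing over the assumed range of 28 to 336 days, and is a few percent for a near-universal event. That the Part 1 columns are exempt rests on reading end of treatment, for those columns, as the end of Part 1 treatment.

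The missing cap at the first Part 2 dose is a separate, generally smaller fault confined to the Part 1 columns. The pulse criterion is a minor error, apparently of direction. All three concern descriptive safety output only.

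**What to change.** Replace both branches in SAP 7.2.4 with one definition for event-free patients:

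t_j = min(last dose + 30, death, data cut-off, and for the P1 columns the day before the first Part 2 dose) - first dose + 1.

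For patients who do not enter Part 2 and whose safety follow-up after the cut-off is included under SAP 2.1, state the window and count events and time over that same window.

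In Table 7.1, change increase to decrease in the combined criterion for pulse at or below 50 bpm.

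The cost is SAP wording and programming. No new data are needed.
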